8.2 Setting and Study Population

8.2.1 Study Period

Enrollment is planned to begin after the launch of sotorasib in South Korea and end after 2 years if enrollment targets are met. A discussion with MFDS will be completed to determine if an extension is required. Subjects will be enrolled on a continuous basis at participating sites. Subjects will be followed from their first dose of sotorasib through completion of 6 months of sotorasib use, discontinuation of sotorasib plus 30 days, withdrawal of consent, death, or lost to follow-up, whichever occurs first.

8.2.2 Selection and Number of Sites

Study sites will include approximately 20 sites that have post-market use of sotorasib.We aim to select almost all sites that prescribe sotorasib.

8.2.3 Subject Professional Eligibility

8.2.3.1 Inclusion Criteria

- subjects prescribed sotorasib in clinical practice according to the approved therapeutic indications, dosage, and administration in South Korea
- subjects or their authorized representative who provide written informed consent to participate in this study

8.2.3.2 Exclusion Criteria

- subjects with contraindications as listed on the approved local label
- subjects concurrently participating in another interventional study will not be allowed to participate in this study
- subject has received any prior treatment with sotorasib before day 1 visit

For analysis of subjects used outside of approved indications, see Section 8.7.

8.2.4 Matching

Not applicable.

8.2.5 Baseline Period

Physical measurements, demographics, and clinical and tumor characteristics will be collected from the initial diagnosis to the initiation of sotorasib use. Treatment history, including prior systemic treatment received will be collected from the advanced diagnosis to the initiation of sotorasib use. Prior and concomitant therapies received will be collected from 1 year before first dose on day 1 through the end of study.

8.2.6 Study Follow-up

Patients will be followed from their first dose of sotorasib through completion of 6 months of sotorasib use, discontinuation of sotorasib plus 30 days, withdrawal of consent, death, or lost to follow-up, whichever occurs first.

8.3 Variables

8.3.1 Exposure Assessment

Sotorasib use:

- indication
- dose
- start date
- end date
- frequency of sotorasib administration
- drug withdrawal of sotorasib any time from the initiation of sotorasib treatment

8.3.2 Outcome Assessment

- Primary outcome measure: Incidence of adverse events, serious adverse events, adverse drug reactions, serious adverse drug reactions, unexpected adverse events, unexpected serious adverse events, unexpected adverse drug reactions, unexpected serious adverse drug reactions, adverse events leading to sotorasib discontinuation, and fatal events throughout the treatment/observation period along with their severity, action taken, and causal relationship with sotorasib will be assessed for any subject who has received at least 1 dose of sotorasib according to the approved therapeutic indications, dosage and administration in South Korea and completed at least 1 safety follow-up. Six-month cumulative subject incidence of the adverse events will be reported and summarized. All adverse events will be graded using the most recent CTCAE version.
- Secondary outcome measure: ORR is defined as the proportion of patients with a BOR of confirmed CR or confirmed PR. To assess ORR, a real-world RECIST based response assessment will be utilized since this is standard for clinic practice in South Korea. Subjects will be categorized according to their BOR during the follow-up period using RECIST criteria v1.1 or a more recent version as noted in the subject's medical records. Subjects will be assigned to one of the following best response categories during each assessment:
 - CR or PR
 - SD
 - PD
 - not evaluable disease (NE)

Each response start date (start date of confirmed PR or better response) or date of disease progression will be assessed at month 2, month 4, and month 6 (EOS visit). Subjects will be followed from their first dose of sotorasib through the completion of 6 months of sotorasib use, discontinuation of sotorasib plus 30 days, withdrawal of consent, death, or lost to follow-up, whichever occurs first.

In addition, investigators should evaluate the clinical outcome of each subject during the surveillance period and assign one of the following descriptions:

- improved
- not changed
- disease progression
- unable to evaluate

8.3.3 Covariate Assessment

- demographics, physical measurements, and smoking status (age, sex, height, weight, smoking history, allergic history, pregnancy, or lactation status)
- clinical and tumor characteristics (date of initial diagnosis, clinical stage, histology, comorbidities [including hepatic impairment and renal impairment], Eastern Cooperative Oncology Group [ECOG] performance score)
- prior systemic treatment received in the advanced disease setting (please refer to the table of data collection)
- sotorasib treatment (please refer to the table of data collection)
- prior and concomitant medications (please refer to the table of data collection)
- adverse events, serious adverse events, adverse drug reactions, serious adverse drug reactions, unexpected adverse events, unexpected serious adverse events, unexpected adverse drug reactions, unexpected serious adverse drug reactions, adverse events leading to sotorasib discontinuation, fatal events, other safety findings, spontaneously reported product complaints.
- treatment response: ORR based on RECIST criteria v1.1, evaluation of investigator (improved, not changed, disease progression, unable to evaluate)

8.3.4 Validity and Reliability

Efforts will be made to collect complete data through the use of clear instructions to investigators regarding the completion of eCRFs. The data collected for this study will be derived from medical records that are kept per routine clinical practice for the documentation and decision-making for a subject's care. The data will be abstracted from the medical records and entered into the eCRF. A detailed data management plan will be implemented to ensure the quality of the collected data.

8.4 Data Sources

The data source for this study is subject medical records. These medical records may include a combination of paper and electronic sources. Study site staff will extract data from the medical records into the study-specific electronic database provided by the sponsor.

8.5 Study Size

Per the most recent MFDS regulatory requirements, the study intends to enroll all eligible subjects in South Korea during the 2 years enrollment period but not less than

25 subjects to collect safety and effectiveness information for the final analysis.

Investigators at participating medical sites are requested to make every effort to enroll

the subjects in a total surveillance method during the enrollment period.

8.6 Data Management

8.6.1 Obtaining Data Files

Data capture for this study is planned to be electronic:

- All source documentation supporting entries into the eCRFs must be maintained and available upon request.
- Updates to eCRFs will be automatically documented through the software's audit trail.

8.6.2 Linking Data Files

Not applicable.

8.6.3 Review and Verification of Data Quality

Automatic checks within the database and further manual review by the sponsor will help to ensure quality and completeness of the data. During this review, subject data is checked for consistency, omissions, and any apparent discrepancies. Data queries will be sent to sites for clarification and resolution of discrepancies.

8.7 Data Analysis

8.7.1 Planned Analyses

8.7.1.1 Interim Analysis/Analyses

According to local regulations, interim analyses will be performed for periodic reporting starting from the initial approval of sotorasib. Periodic reports are submitted to the health authority every 6 months for the first 2 years and every year thereafter until the end of the study period.

8.7.1.2 Final Analysis

The final analysis will be conducted when the last enrolled subject reaches the EOS. A snapshot of the finalized database will be used for analysis. All analyses will be performed using SAS[®] 9.4 or later versions. Safety and effectiveness data collected at scheduled time points will be used for analysis.

The Safety Analysis Set will include all subjects who received at least 1 dose of sotorasib in accordance with the approved therapeutic indications, dosage, and administration in South Korea and completed at least 1 safety follow-up. The safety analysis will be the analysis conducted using the Safety Analysis Set, and will describe the following assessments:

- adverse events
- serious adverse events
- adverse drug reactions
- serious adverse drug reactions
- unexpected adverse events
- unexpected serious adverse events
- unexpected adverse drug reactions
- unexpected serious adverse drug reactions
- adverse events leading to sotorasib discontinuation
- fatal events

The Full Analysis Set (ie, Effectiveness Analysis Set) will include all subjects from the Safety Analysis Set who have at least 1 follow-up tumor assessment to estimate the ORR after initiation of sotorasib. Subjects will be followed from their first dose of sotorasib through the completion of 6 months of sotorasib use, discontinuation of sotorasib plus 30 days, withdrawal of consent, death, or lost to follow-up, whichever occurs first. In addition, investigators should evaluate the clinical outcome of each subject during the surveillance period and assign one of the following descriptions:

- improved
- not changed
- disease progression
- unable to evaluate

The data of subjects used outside of the approved indication will be analyzed separately.

The study protocol does not define exact referral dates for follow-up visits.

Follow-up visits occur during routine practice. The investigator documents the date of initial visit and follow-up in the eCRF and follows the study procedures pertaining to data collection for the visit.

8.7.2 Planned Method of Analysis

8.7.2.1 General Considerations

The statistical analysis in this post-marketing study will be descriptive in nature, and no hypothesis testing will be performed. Categorical outcomes will be summarized by the number and percentage of subjects in each category. Continuous outcomes will be summarized by the number of non-missing values, mean, standard deviation, median, lower and upper quartiles, and minimum and maximum values. Subject incidence will be summarized for adverse events, serious adverse events, adverse drug reactions,

serious adverse drug reactions, unexpected adverse events, unexpected serious adverse events, unexpected adverse drug reactions, unexpected serious adverse drug reactions. Also, 95% CI will be presented based on exact method for incidence. ORR will be reported with a Clopper-Pearson exact confidence interval.

Difference in safety or effectiveness results by subject's background factor can be analyzed by Chi-square test and to estimate factors that may affect the safety or effectiveness results, multivariate analysis can be conducted.

Additional information will be collected according to the RMP when adverse events related to the Important Safety Specification Requiring Further Evaluation Items in RMP are collected. The special investigation group (elderly, children, hepatic impairment, renal impairment, pregnancy, or lactation) will be analyzed separately.

All adverse events are tabulated in the report using the latest version of Medical Dictionary for Regulatory Activities (MedDRA), using System Organ Class (SOC) and Preferred Term (PT).

8.7.2.2 Missing or Incomplete Data and Lost to Follow-up

Missing safety data will not be imputed as a general rule; analysis will be based on available data.

8.7.2.3 Descriptive Analysis

8.7.2.3.1 Description of Study Enrollment

Physicians will evaluate patients and determine if treatment with sotorasib is appropriate in accordance with local standards and the approved sotorasib indication. The decision to treat the patient with sotorasib should be made independently of, and before, enrollment in the study. Once treatment with sotorasib has been selected, the investigator or an assigned delegate can discuss the details of the study with the prospective subject. Each prospective patient is assessed for eligibility. Once the eligibility conditions are met, which includes signing the consent, the subject will be formally enrolled into the study.

8.7.2.3.2 Description of Subject Characteristics

Baseline characteristics and assessments will be made during the baseline period. Subject characteristics including physical measurements, demographics, smoking status, treatment history as well as clinical and tumor characteristics will be collected during the baseline period by the investigator or a designated representative and will be summarized using descriptive statistics. Refer to Table 1 for a schedule of data collection.

8.7.2.4 Analysis of Primary, Secondary, and Exploratory Endpoint(s)8.7.2.4.1 Analysis of Primary Endpoint

Safety Analysis: The Safety Analysis Set will contain all subjects who have received at least 1 dose of sotorasib in accordance with the approved therapeutic indications, dosage and administration in South Korea and completed at least 1 safety follow-up. The report will include treatment-emergent, treatment-related adverse events and serious adverse events. The reports will use the standard SOC and PT system and will use the most recent CTCAE grading system. Subject listing of all adverse events, serious adverse events, adverse drug reactions, serious adverse drug reactions, unexpected serious adverse events, unexpected serious adverse events leading to sotorasib discontinuation, and fatal events will also be included. All adverse events and serious adverse events will be summarized using descriptive methods. If an adverse event will be presented. Frequencies and percentages for discrete variables; mean, standard deviation, median, minimum, and maximum values for continuous variables will be reported.

8.7.2.4.2 Analysis of Secondary Endpoint

Effectiveness Analysis: Investigators will use the RECIST criteria v1.1, or a more recent version if available, to assess the tumors based on magnetic resonance imaging or computed tomography scans beginning at the baseline and succeeding visits as part of routine clinical practice. Based on all the available data and for each time point post-baseline, the site investigator will classify the tumors into one of the categories: CR, PR, SD, PD or NE. The number and percentage of subjects with a BOR of CR, PR, SD, and PD will be presented. The ORR (%) across all timepoints = ([Number of BOR of confirmed CR + Number of BOR of confirmed PR]/Total number treated) x 100. In addition, investigators should evaluate the clinical outcome of each subject during the surveillance period and assign one of the following descriptions:

- improved
- not changed
- disease progression
- unable to evaluate

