Per the most recent MFDS regulatory requirements, the study intends to enroll all eligible subjects in South Korea during the 2 years enrollment period but not less than 25 subjects to collect safety and effectiveness information for the final analysis. Investigators at participating medical sites are requested to make every effort to enroll subjects in a total surveillance method during the enrollment period.

• Data Analysis

The data will be summarized descriptively.

The Safety Analysis Set will include all subjects who received at least 1 dose of sotorasib in accordance with the approved therapeutic indications, dosage, and administration in South Korea and completed at least 1 safety follow-up. The incidence of adverse events will be summarized to include all treatment-emergent adverse events recorded from the start of sotorasib on this study or any worsening of medical conditions initially experienced before initiation of this study. All adverse events will be graded using the most recent Common Terminology Criteria for Adverse Events (CTCAE) version. This summary for adverse events will be performed for the following categories:

- all adverse events and adverse drug reactions
- serious adverse events and serious adverse drug reactions
- unexpected adverse events and unexpected adverse drug reactions
- unexpected serious adverse events and unexpected serious adverse drug reactions
- adverse events leading to sotorasib discontinuation
- fatal events

The 6-month cumulative incidence of adverse events will be presented as frequency and percentage.

The Full Effectiveness Analysis Set will include all subjects from the Safety Analysis Set who also have at least 1 follow-up tumor assessment to estimate the ORR after initiation of sotorasib. In addition, the investigators should evaluate the clinical outcome of each subject during the surveillance period.

Subjects will be followed from their first dose of sotorasib through completion of 6 months of sotorasib use, discontinuation of sotorasib plus 30 days, withdrawal of consent, death, or lost to follow-up, whichever occurs first.

The study protocol does not define exact referral dates for follow-up visits.

Follow-up visits occur during routine practice. The investigator documents the date of initial visit and follow-up in the electronic case report form (eCRF) and follows the study procedures pertaining to data collection for the visit.

5. Amendments and Updates

None

6. Rationale and Background

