Safety events*: Unexpected adverse events, unexpected serious adverse events, unexpected adverse drug reactions, and unexpected serious adverse drug reactions will be analyzed from the collected adverse events/serious adverse events/adverse drug reactions/serious adverse drug reactions as part of a special analysis.

^a Baseline and day 1 assessments can occur on the same day.

^b Tumor assessment will not be completed at Day 21

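### The protocol fixes two incompatible denominators for the ORR: all treated subjects in the formula, and subjects with a follow-up scan in the analysis set

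*Protocol*

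**What the plan says.** Section 8.7.2.4.2 of the protocol gives the only explicit ORR formula. It adds confirmed complete and confirmed partial responses and divides by everyone treated: "Number of BOR of confirmed PR]/Total number treated) x 100".

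Section 8.7.1.2 defines the Effectiveness Analysis Set as "all subjects from the Safety Analysis Set who have at least 1 follow-up tumor assessment to estimate the ORR after initiation of sotorasib". The Abstract (Section 4, Data Analysis) does the same: "all subjects from the Safety Analysis Set who also have at least 1 follow-up tumor assessment to estimate the ORR". That set is nested in the Safety Analysis Set, whose members must also have "completed at least 1 safety follow-up".

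Sections 8.1 and 8.3.2 define the ORR as a proportion of patients and name no analysis set, so they do not settle the matter. Section 8.7.2.1 plans a Clopper-Pearson interval for the ORR. The missing-data rule in Section 8.7.2.2 covers safety data only.

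On timing, footnote b of Table 1 states: "Tumor assessment will not be completed at Day 21". Section 8.3.2 places response assessment at months 2, 4 and 6. On presentation, Section 8.7.2.4.2 states: "The number and percentage of subjects with a BOR of CR, PR, SD, and PD will be presented". The not-evaluable category, which the same section allows at each time point, is absent from that sentence.

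**The concern.** The same data can yield two different ORRs, depending on which section the programmer follows. This is not detail that can be left to an analysis plan. The protocol itself fixes both denominators, and no analysis plan can honour both.

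The choice also has a direction. Subjects without a follow-up scan will include some who die, stop treatment or are lost before the first expected tumor assessment at about month 2. Under Section 8.2.6 their follow-up may already have ended by then, and Section 8.9.3 accepts that discontinuation may be informative about outcome. Removing them from the denominator conditions the ORR on having reached a scan.

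The final report goes to the regulator (Section 12), the results are to be published (Section 12.1), and Section 8.9.2 expects them to extend to patients treated with sotorasib in South Korea. An ORR confined to scanned subjects describes a narrower group than that.

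**Working it through.** **Is there a figure to reproduce?** The protocol states no expected ORR, precision or power for this study, and Section 8.5 presents the minimum of 25 subjects as a regulatory requirement. The only response rate is the pivotal-study reference in Section 6.1: 37.1% (95% CI 28.6 to 46.2). Searching sample sizes from 20 to 399, the one Clopper-Pearson interval that matches it is 46/124. That denominator is inferred, not stated, so 37.1% serves here only as a convenient starting rate.

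**Candidate denominators, widest first**

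| Denominator | Source | Requires |
|---|---|---|
| Treated | 8.7.2.4.2 | at least 1 dose |
| Safety Analysis Set | 8.7.1.2 | dose on label, plus a safety follow-up |
| Effectiveness Analysis Set | 4, 8.7.1.2 | the above, plus a follow-up tumor assessment |

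The first and third are the ones tied to the ORR.

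**Formula.** Let N be the number treated, x the confirmed responders, and d the share of N without a follow-up scan. A confirmed response needs follow-up scans, so x is the same under both readings.

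- Treated-based ORR = x/N
- Scan-based ORR = x/(N(1-d))
- Ratio = 1/(1-d)

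The ratio is 1 when d = 0 and above 1 otherwise. The scan-based ORR can never be the lower of the two.

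**Rates, with d assumed and a treated-based ORR of 37.1%**

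| d | Scan-based ORR | Difference |
|---|---|---|
| 5% | 37.1/0.95 = 39.1% | +2.0 points |
| 10% | 37.1/0.90 = 41.2% | +4.1 points |
| 20% | 37.1/0.80 = 46.4% | +9.3 points |

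**Counts at the minimum size, N = 25 with 9 responders (Clopper-Pearson; 95% level assumed)**

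| Without a scan | ORR | 95% CI |
|---|---|---|
| treated-based | 9/25 = 36.0% | 18.0 to 57.5 |
| 1 | 9/24 = 37.5% | 18.8 to 59.4 |
| 3 | 9/22 = 40.9% | 20.7 to 63.6 |
| 5 | 9/20 = 45.0% | 23.1 to 68.5 |

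**A larger study, N = 100 with 37 responders.** The treated-based ORR is 37.0% (27.6 to 47.2). With 12 subjects unscanned the scan-based ORR is 37/88 = 42.0% (31.6 to 53.0). The gap does not shrink with sample size, although the intervals do.

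Section 8.7.2.1 attaches the 95% level to the incidence interval and names only the method for the ORR, hence the assumed level above.

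**The case against.** The strongest reply is that the explicit formula, read literally, drops nobody, so the ORR is inflated only if the analysis-set definition overrides it. That is correct, and the point is limited accordingly. It does not remove the conflict, because both definitions state that they serve the ORR. A sponsor might say that the treated total means treated members of the Effectiveness Analysis Set, but the text does not say so.

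Several stronger readings are tempting and are not supported:

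- A reader might infer that everyone who fails before month 2 is removed. Footnote b excludes day 21 only, Section 8.7.1.2 leaves visit dates to routine practice, and follow-up runs 30 days past discontinuation. An earlier unscheduled scan is possible, and a subject who stops after about month 1 may still be followed at month 2. Nor is every unscanned subject a treatment failure. None of them, however, can be a confirmed responder.
- A reader might infer that the ORR is the only quantified effectiveness result. Best-response categories get counts and percentages in Section 8.7.2.4.2, and Section 8.7.2.1 extends this to all categorical outcomes, including the investigator's clinical outcome. The ORR is only the one effectiveness endpoint with a formula and a named interval.
- A reader might infer that the investigator's clinical outcome is confined to scanned subjects, which would empty its could-not-be-evaluated category. No section imposes that limit. The inference rests on where a sentence sits in Section 8.7.1.2, and the text asks for the evaluation in each subject.
- The missing not-evaluable row may be a slip, since Section 8.3.2 lists that category and Section 8.7.2.1 asks for every category. It also differs from having no scan at all, since it is a classification given at an assessment.

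The unscanned shares used above have no basis in the protocol, and at N = 25 the intervals overlap heavily. Both remarks stand. They bear on the size of the effect, not its direction.

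**Conclusion.** The contradiction is real and the protocol does not resolve it. If the scan-based set is used and any treated subject lacks a follow-up scan, the reported ORR exceeds the treated-based ORR by the factor 1/(1-d), provided there is at least one responder. The direction follows from arithmetic. The size depends wholly on d, and the range shown, 2.0 to 9.3 points, rests on assumed values of 5% to 20% and on a borrowed rate of 37.1%.

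This should be fixed, but it does not undermine the study. The design is descriptive with no hypothesis test, safety is the primary objective, and the ORR is secondary. The repair can be made before analysis without new data.

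**What to change.** - Keep the denominator in Section 8.7.2.4.2 for the main ORR, and define it: all enrolled subjects who received at least 1 dose within the approved indication, with no requirement for a follow-up scan or a safety follow-up. Substituting the Safety Analysis Set would not do, because its safety follow-up condition can itself exclude early losses.
- Count subjects classed as not evaluable, and those with no post-baseline assessment, as non-responders in that ORR.
- Add a not-evaluable/not-assessed row to the best-response table so that its rows account for the whole denominator.
- Report the ORR in subjects with at least 1 follow-up tumor assessment as a labelled supportive analysis.
- Align the Abstract, Section 8.7.1.2 and Section 8.7.2.4.2 with these rules.

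The cost is a wording change, one extra table and a main ORR that may be lower than the scan-based figure. No additional data collection is needed.
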